#### 15.1.4 Adverse Device Effect / Serious Adverse Device Effect

An adverse device effect is an AE related to the use of the investigational medical device.

NOTE 1- This includes any AE resulting from insufficiencies or inadequacies in the IFU, the deployment, the implantation, the installation, the operation, or any malfunction of the investigational medical device.

NOTE 2- This includes any event that is a result of a use error or intentional abnormal use of the investigational medical device.

A SADE is an adverse device effect that has resulted in any of the consequences characteristic of an SAE.

#### 15.1.5 Unanticipated (Serious) Adverse Device Effect

An Unanticipated Adverse Device Effect (UADE) or Unanticipated Serious Adverse Device Effect (USADE) is any SAE on health, safety, any life-threatening problem, or death caused by, or associated with a device, if that effect, problem, or death was not previously identified in nature, severity, or degree of incidence in the investigational plan or risk analysis report, or any other unanticipated serious problem associated with a device that relates to rights, safety, or welfare of subjects. Refer to table 10 for a comprehensive list of foreseeable and anticipated AEs.

### 15.1.6 Study Device Deficiency, Failure or Malfunction

A device deficiency means any inadequacy in the identity, quality, durability, reliability, usability, safety or performance, including of an investigational device, including

- Malfunction (failure to perform in accordance to its intended purpose when used in accordance with the IFU/CIP/IB),
- Use errors,
- Inadequacy in labelling (for studies under MDR2017/745 in inadequacy in information supplied by the manufacturer (including labelling)).

If a device failure is detected or suspected, it should be documented on the appropriate eCRF and device failure and AE must be reported per section 15.4.1 AE documentation and reporting requirements.

## 15.2 Classification of an Adverse Event

### 15.2.1 Severity of Event

The intensity or severity of each AE must be assessed according to the following classifications:

**Table 7: Intensity or Severity Definitions**

Mild	Awareness of signs, symptoms, or events that are otherwise easily tolerated that may result in minimal transient impairment of a body function or damage to a body structure, but do not require intervention other than monitoring.
Moderate	Any event that results in moderate transient impairment of a body function or damage to a body structure that causes interference with usual activities, or that warrants possible intervention, such as the administration of medication, to prevent permanent impairment of a body function or damage to a body structure.
Severe	Any event that is incapacitating (an inability to do usual activities) or is life-threatening and results in permanent impairment of a body function or damage to a body structure, or requires intervention, such as major surgery, to prevent permanent impairment of a body function or damage to a body structure.

### 15.2.2 Relationship to Study Device

For all collected AEs, the clinician who examines and evaluates the participant will determine the AEs causality based on temporal relationship and his/her clinical judgment. The degree of certainty about causality will be graded using the categories below as described per Medical Device Directive Guidance (MEDDEV) 2.7/3.

**Table 8: Adverse Event Causality Classifications**

Caused By	Relation	Definition of Relation
Device	Definitely (Causal Relationship)	The event is associated with the investigational device beyond reasonable doubt
	Probable	The relationship with the use of the investigational device seems relevant and/or the event cannot be reasonably explained by another cause, but additional information may be obtained
	Possibly	The relationship with the use of the investigational device is weak but cannot be ruled out completely
	Unlikely	The relationship with the use of the investigational device seems not relevant and/or the event can be reasonably explained by another cause, but additional information may be obtained
	Not related	Relationship to the investigational device can be excluded
Study Procedure	Definitely (Causal Relationship)	The event is associated with the study procedure beyond reasonable doubt
	Probable	The relationship with the study procedure seems relevant and/or the event cannot be reasonably explained by another cause, but additional information may be obtained
	Possibly	The relationship with the study procedure is weak but cannot be ruled out completely
	Unlikely	The relationship to the study procedure seems not relevant and/or the event can be reasonably explained by another cause, but additional information may be obtained
	Not related	Relationship to the procedure can be excluded

### 15.2.3 Outcome

The outcome of each AE must be assessed according to the following classifications:

**Table 9: Adverse Event Outcome Classifications**

Classification		Definition
Resolved without sequelae		Subject fully recovered with no observable residual effects
Resolved with sequelae		Subject recovered with observable residual effects
Ongoing	Improved	Subject's condition improved, but residual effects remain
	Unchanged	AE is ongoing without changes in the overall condition
	Worsened	Subject's overall condition worsened
Death		Subject died as a result of the AE (whether or not the AE is related to the device or procedure)

### 15.2.4 Expectedness (Anticipatedness)

An anticipated AE is an effect which by nature, incidence, severity or outcome has been identified as a possible complication associated with the investigational medical device and/or intervention procedure.

Potential AEs that are reasonably anticipated to occur during the cardiac EP procedure are listed in table 10. These events should be reported via EDC as anticipated AEs. Anticipated AEs are to be reported to the sponsor via EDC as indicated in section 15.4.

**Table 10: Comprehensive List of Anticipated Adverse Events**

Anticipated Adverse Events	
(Acute) renal failure	Infection, systemic
(Aspiration) pneumonia	Inflammation
(Skin) laceration	Isolated ST segment elevation
(Vascular) bleeding	Liver toxicity
Acute Respiratory Distress Syndrome (ARDS)	Local Hematoma/ecchymosis
Air embolism	Localized skin reaction
Allergic reaction to contrast media	Mitral Insufficiency
Allergic skin reaction	Myocardial infarction with or without ST elevation
Altered Mental Status Confusion; Altered Level of Consciousness;	Nausea
Anaphylactic shock	Neurological disorders (poor coordination)
Anemia	Neurological disorders (tremor)
Anesthesia complications/reactions	Neuropraxia/Muscle contraction
Anoxic or hypoxic encephalopathy	Palpitations
Aortic Puncture	Papillary Muscle tear/injury
Apnea - sedation induced	Pericardial effusion resulting in tamponade
Arrhythmia (new or worsening of pre-existing arrhythmia)	Pericardial effusion without tamponade
Asthmatic attack	Pericarditis
Asymptomatic Cerebral Emboli	Periesophageal vagal nerve injury
Atelectasis	Peripheral nerve injury
Atrial fibrillation	Phlebitis
Atrial Septal Defect (acquired)	Phrenic nerve damage/injury
Atrio-Esophageal fistula	Pleural effusion
Auditory Disorder	Pneumothorax
AV fistula	Post- and perioperative pain
Back Pain	Post Procedural Hematuria
Bone disorder	Pseudoaneurysm
Bronchial fistula, Broncho-pericardium fistula	Pulmonary edema
Cardiac arrest	Pulmonary embolism
Cardiac pacemaker insertion or replacement	Pulmonary hypertension
Cardiac perforation	Pulmonary toxicity, like acute pulmonary syndrome
Cardiac Valve Rupture/Damage	Pulmonary vein dissection
Cardiogenic Shock	Pulmonary vein stenosis
Cerebro-Vascular accident (CVA)/Stroke	Renal Artery Stenosis
Chest pain/discomfort	Respiratory arrest
Complete or incomplete heart block	Respiratory depression

Conduction block	Respiratory failure
Coronary Artery Stenosis	Respiratory infection
Coronary artery thrombosis	Retinal Artery Embolism
Death	Retroperitoneal bleeding
Deep venous thrombosis	Rhabdomyolysis, including produced by body position or propofol
Diaphragmatic paralysis	Sedation induced CO 2 retention with lethargy and cholecystitis
Dislodgement/Malfunction of pacemaker/defibrillator leads	Seizure
Disseminated Intravascular Coagulation	Sepsis
Dizziness, presyncope, vertigo	Sinus bradycardia
Dysphagia	Sinus tachycardia
Dyspnea	Skin burn or necrosis
Endocarditis	Skin discoloration
Epigastric Distress	Skin edema
Epistaxis	Skin or soft tissue (radiation) injury/tear
Esophageal injury / perforation	Subclavian artery puncture
Expressive aphasia	Temperature elevation / Fever
Fatigue	Thrombocytopenia
Gastric hypomotility	Thromboembolism
Gastroesophageal reflux	Thrombosis
Gastrointestinal disorders	Thyroid disorders
Gastrointestinal diverticulosis	Toxic reaction
Gastroparesis	Transient extremity numbness
Headache	Transient Ischemic attack (TIA)
Heart failure (acute or chronic)	Urinary Retention Postoperative
Heart injury	Urinary tract injury or infection related to the urinary catheter
Heart valve insufficiency	Valvular damage/insufficiency
Hemoptysis	Vascular (access) dissection (including coronary arteries)
Hemorrhage	Vascular occlusion
Hemothorax	Vasovagal reactions
High/increased creatine phosphokinase (CPK)	Ventricular Fibrillation
Hypertension	Vessel damage/trauma
Hypervolemia	Vessel perforation
Hypotension	Vessel spasm (including coronary arteries)
Hypovolemia	Visual disturbance
Hypoxia	Worsening of pre-existing pulmonary disease
Increased phosphokinase level	Wound healing disturbance
Infection, localized	

\*Atrial Fibrillation and exacerbation of an existing arrhythmia are anticipated adverse events. However, they will not be captured as such under this protocol, as they are considered recurrence of disease.

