**Infection:** The percutaneous procedure carries risk of infection, either at the catheter insertion site or systemically, including endocarditis and septic emboli (risk <0.5%). This risk can be minimized by using standard aseptic technique and, when indicated, by the use of antibiotic agents.

**Allergic Reaction:** A patient could develop an allergic reaction and/or inflammation due to the local anesthetic, sedatives, x-ray dye, heparin, protamine, or other agents administered during the procedure (risk <1%). The If an allergic reaction occurs, typical standard of care precautions should be taken.

**Ventricular Tachycardia:** Ventricular Fibrillation or other arrhythmia: The literature suggests that in some instances PFA energy could induce ventricular tachycardia, ventricular fibrillation (ventricular rate usually >300 bpm), or another arrhythmia. Care should be taken to carefully monitor the patient's ECG recordings throughout the procedure.

**Muscular Nerve Injury:** Pulse field ablations have been associated with muscular contraction in the literature. These contractions can cause acute or post procedural patient discomfort. Patient comfort should be maintained through local pain management standards of care.

**Hypervolemia/Fluid Overload:** The Circular IRE Catheter is an irrigated catheter. Excessive use of irrigation could cause hemodynamic imbalance. To prevent hypervolemia, ensure that the catheter is used per its instructions for use.

**Risk due to Arcing:** The hazard of arcing of energy creates a risk for patient injuries including Cardiac Arrest, burns, papillary muscle rupture, valve rupture, or cardiac perforation. To prevent such harms, the physician should use the catheter and generator per their intended directions for use.

**Pulmonary injury:** Pulmonary injuries, such as pneumothorax, may be caused by thermal injury during traditional RF injury. As pulsed field ablation is a non-thermal modality, this injury is not expected to occur. However, to keep the risk of pulmonary injuries low, energy should delivery should be halted after ECG signals have been sufficiently attenuated.

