#### 15.1.1 Definition of Adverse Events (AE)

An AE is any untoward medical occurrence in a subject whether or not related to the investigational device.

Specifically, an AE is **any** undesirable experience (sign, symptom, illness, abnormal laboratory value, or other medical event) occurring to a subject during the course of the study, whether or not it is related to the investigational device or procedure. Physical findings (including vital signs) observed at follow-up, or pre-existing physical findings that worsen compared to baseline are considered AEs.

[figure not shown]
Any medical condition that is present at the time that the participant is screened will be considered as baseline and not reported as an AE. Such conditions should be added to background medical history, if not previously reported. However, if the study participant's condition deteriorates at any time during the study, it will be recorded as an AE.

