#### Following arrhythmia's do not meet the definition of an AE:

- AF recurrence by itself is considered a recurrence of disease (pre-existing condition)
- Recurrence of pre-existing or underlying (treated during index procedure) AFL/AT is considered as a recurrence of disease
- Onset of non-previously identified AFL/AT which was treated during the index procedure as underlying arrhythmia (pre-existing condition)
- Re-ablation for AF or any pre-existing AFL/AT, however any procedural complication is considered an AE and shall be reported within the applicable timelines.
- Re-ablation for any non-pre-existing (underlying) AFL/AT which was treated during the index procedure, however any procedural complication is considered an AE and shall be reported within the applicable timelines.
- Cardioversion (pharmacological or synchronized electrical) for AF/AFL/AT recurrence during the hospitalization for the index ablation procedure, or throughout the duration of the study.

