#### Following arrhythmia's meet the definition of an AE:

- Onset of non pre-existing AFL/AT which was not treated during the index procedure.

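### The Table 10 footnote removes more arrhythmia worsening from adverse event capture than the exceptions in Protocol 15.1.1 allow

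*Protocol*

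**What the plan says.** Three places in Protocol section 15 govern whether a worsened arrhythmia is recorded.

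- **Section 15.1.1** gives the general rule: if the participant's "condition deteriorates at any time during the study, it will be recorded as an AE". It then lists arrhythmias that are not AEs. These are AF recurrence taken alone, recurrence of pre-existing or underlying AFL/AT, "Onset of non-previously identified AFL/AT which was treated during the index procedure as underlying arrhythmia (pre-existing condition", re-ablation for these arrhythmias, and cardioversion for their recurrence. Complications of a re-ablation remain AEs. A second, one-line list names what does count: "Onset of non pre-existing AFL/AT which was not treated during the index procedure".
- **Section 15.2.4** says of the events in Table 10: "These events should be reported via EDC as anticipated AEs". The table lists atrial fibrillation and also "Arrhythmia (new or worsening of pre-existing arrhythmia".
- **The Table 10 footnote** says: "Atrial Fibrillation and exacerbation of an existing arrhythmia are anticipated adverse events. However, they will not be captured as such under this protocol". The same sentence gives disease recurrence as the reason.

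**The concern.** A site with a subject whose existing arrhythmia has become worse finds one instruction to record it (15.1.1, and 15.2.4 with the table row) and another not to (the footnote). The counts then depend on which instruction the site follows, and the footnote can only lower them.

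The footnote's reason does not cover its own scope. Recurrence means that the old disease has come back. Worsening means that something is worse than at baseline, and that is where a device effect would have to be looked for. The study is single-arm and premarket, so its descriptive safety tables have no concurrent control against which under-recording would show.

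The two arrhythmia lists in 15.1.1 raise a related difficulty. For AFL/AT first seen at the index procedure, they can be read as making AE status depend on whether the operator ablated it.

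**Working it through.** No arithmetic applies, because the point rests on no rate, sample size or error level. The check sets the rules side by side.

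**Step 1. Compare the rules by type of event.**

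| Event | 15.1.1 | Table 10 with 15.2.4 | Footnote | Result |
|---|---|---|---|---|
| Plain AF recurrence | Not an AE | AF is listed | Not captured | Footnote agrees with 15.1.1 |
| Recurrence of pre-existing AFL/AT | Not an AE | No row for plain recurrence | Not captured if seen as recurrence | Footnote agrees with 15.1.1 |
| AF or AFL/AT worse than at baseline, beyond recurrence | AE under the deterioration rule; no exception names worsening | Reportable | Not captured | Conflict |
| Worsening of an existing arrhythmia other than AF/AFL/AT | AE; no exception covers it | Reportable | Not captured | Conflict |
| New ventricular arrhythmia | AE | Reportable | Not mentioned | AE under all three |

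The footnote is wider than 15.1.1 in the third and fourth rows only.

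**Step 2. Follow the loss of AE status to the endpoints.**

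- Section 15.1.4 defines an adverse device effect as an AE related to the device, and a serious adverse device effect (SADE) as a subset of those. An event that is not an AE can be neither.
- Section 15.2.2 grades causality for collected AEs, so an uncollected event is not assessed for relation to the device.
- SADEs, SAEs by time window and non-serious AEs are additional safety endpoints (Protocol 8.2.3; section 7.6.2 of both SAPs). Loss from the SADE and non-serious counts follows directly.
- Loss from the SAE counts is possible but not certain. Section 15.1.2 defines an SAE as any event meeting its criteria and repeats no arrhythmia exception.
- The primary safety composite (Protocol 8.2.1) lists no arrhythmia. The comparison with the 14% performance goal, its power and its type I error do not depend on this point.

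**Step 3. See whether another route collects the same events.** Section 14.3 collects cardiac hospitalizations and cardioversions, and the schedule collects repeat ablations. Hospitalizations and cardioversions collected this way carry no causality grade, and neither SAP specifies an analysis of them. Arrhythmia monitoring starts at month 3, and Appendix 1 does not count recurrence in the blanking period as a failure. Early worsening handled under the footnote can therefore be absent from both the AE counts and the effectiveness endpoint.

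**Step 4. Read the two AFL/AT lists in 15.1.1 together.** The first exempts AFL/AT not identified before, if it was treated at the index procedure as an underlying arrhythmia. The second makes AFL/AT that is not pre-existing an AE if it was not treated. A further line exempts re-ablation for AFL/AT that it calls both non-pre-existing and underlying, again if treated at index. The situation is foreseeable: section 14.2.2.2 provides for an arrhythmia outside the PV region found after the study catheter is inserted. Nothing in 15.1.1 says how the judgement that it was underlying is made or recorded.

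**The case against.** The strongest reply is that the footnote restates 15.1.1. Its full second sentence reads "However, they will not be captured as such under this protocol, as they are considered recurrence of disease", which is the ground on which 15.1.1 exempts AF and AFL/AT recurrence. It is also written as an exception to its own table. For plain recurrence, the commonest arrhythmia event to expect in this population, footnote and definition agree. That stands, and it confines the conflict to two rows of the comparison. It does not remove the conflict, because the footnote names worsening and limits it to no particular arrhythmia.

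It is also fair that the affected endpoints are descriptive, that the primary test is untouched, and that patients known to need ablation for ventricular tachycardia are excluded. The population in the fourth row is therefore small.

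Two stronger readings are tempting:

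- **Ventricular arrhythmia provoked by the device goes unrecorded.** Section 6.4.1 warns that "PFA energy could induce ventricular tachycardia, ventricular fibrillation". That passage concerns induction. A new ventricular arrhythmia remains reportable under Table 10, and the footnote does not exempt it.
- **AFL/AT provoked by pulsed field energy and then ablated can never be an AE.** The exemption requires treatment as an underlying arrhythmia, which can be read as needing a judgement that it was already there. The text is ambiguous; it does not establish that such events are always lost.

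**Conclusion.** The inconsistency is real and should be corrected, but it is narrow. The footnote excludes worsening beyond recurrence, and worsening of arrhythmias other than AF/AFL/AT, neither of which the 15.1.1 exceptions cover. Where sites follow the footnote, those events are missing from the SADE and non-serious AE counts and possibly from the SAE counts. The direction is toward fewer recorded events. The AFL/AT lists are a second ambiguity of the same kind.

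The size cannot be given. A reader might start from the planned 65% effectiveness, take the remaining 35% as subjects with recurrence, and assume that some fraction had a serious worsening. The documents do not support this. The 35% also contains acute procedural failures and counts any documented episode of at least 30 seconds, including asymptomatic ones. No document gives a rate of serious or device-related worsening.

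The conclusion assumes that at least some sites apply the footnote as written rather than reading it down to the 15.1.1 list.

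**What to change.** 1. Limit the Table 10 footnote to the exceptions listed in 15.1.1, by cross-reference. State that worsening of any other existing arrhythmia, and worsening beyond recurrence that is serious or judged device-related, is recorded as an AE or SAE. Ask the investigator for the relatedness judgement on such events, since 15.2.2 otherwise requests it only for AEs already collected.
2. Reconcile the two AFL/AT lists in 15.1.1. The AE status of AFL/AT first seen at the index procedure should depend on whether it was judged pre-existing, with the basis for that judgement recorded, and not on whether it was ablated.

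The cost is two wording changes in section 15 and a note to sites. Some more AEs will be recorded. Treatment, the primary endpoints and the planned SAP tables stay as they are.

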### **15.3 Time Period and Frequency for Event Assessment and Follow-up**

The investigator, or designated individual, will record all reportable events with start dates occurring any time after informed consent is obtained. At each study visit, the investigator will inquire about the occurrence of AEs/SAEs since the last visit.

All AEs, especially SAE's, need to be followed until the event is resolved (with or without sequelae), stabilization, or until the event is adequately explained. The medical monitor or designee of this clinical investigation will decide if more follow-up information is needed in case the event is not resolved at study completion. All required treatments and outcomes of the SAE must be recorded in the eCRF.

### **15.4 Reporting Procedures**

#### **15.4.1 Adverse Event Documentation and Reporting Requirements**

Subjects should be encouraged to report AEs spontaneously or in response to general, non-directed questioning (e.g. "How was your health been since last visit?"). Anytime during the study, the subject may volunteer information that resembles an AE.

Each AE must be reported to the sponsor regardless of classification, seriousness, intensity, outcome or causality. The investigator is responsible for ensuring that all AEs observed by the investigator, or reported by the subject, that occur from the time that the subject has signed the informed consent through the end of the study are properly assessed, recorded, and reported as defined and described in the AEs, Adverse Device Effects and Device Deficiencies section of this protocol (section 15). All AEs must be documented by completing subject's medical records (source documents) and appropriate eCRF by the investigator or study coordinator throughout the study and provided to the Sponsor. All AEs will be monitored until they are adequately resolved or explained.

Anonymized documentation pertaining to the AE (e.g. laboratory tests, consultation reports, post-mortem reports, new information relating to a previously reported AE, correspondence with the local EC, etc.) will be provided by the investigator to the sponsor or designee in a timely manner, when requested. Follow-up reports relative to the subject's subsequent course must be submitted to the sponsor or designee until the event has resolved or, in case of permanent impairment, until the condition stabilizes. If the subject is withdrawn from the study because of the AE, the information must be included on the appropriate eCRFs.

The Sponsor is responsible for the classification of AEs and ongoing safety evaluation of the study and shall review the investigator's assessment of all AEs. The sponsor will determine and document in writing their seriousness and relationship to the investigational device. In case of disagreement between the sponsor and the PIs, the sponsor shall communicate both opinions to the concerned parties.

Biosense Webster will ensure that investigators are instructed to return devices suspected of causing an AE or SAE (i.e., definitely (causal relationship) device-related or possibly device-related) in accordance with relevant regulations and current company procedures.

In the case of serious device effects and device deficiencies that could have led to SAEs, the Sponsor will determine whether the risk analysis needs to be updated and whether corrective or preventative action is required.

Timing for reporting the different types of AEs is described in table 11.

